9.2.2 Safety endpoints

9.2.2.1 *Adverse events*

Refer to [Section 10.4](#) to [Section 10.6](#) for details.

9.2.2.2 *Laboratory safety variables*

Hematology, chemistry, urinalysis, and serum pregnancy testing samples will be analyzed by a central laboratory. The urine pregnancy test kit will be provided to the site by the laboratory.

Blood samples for serum chemistry and hematology testing will be collected to measure overall patient health at screening. Total basophil and eosinophil counts are of particular interest in AD patients, due to the occurrence of basophil histamine release and eosinophilia in this population.

Understanding the lymphocyte profiles of AD patients may help researchers understand disease heterogeneity. Blood samples should be collected after a 6 to 8 hour fast, if possible; fasting is not mandatory. Detailed instructions for blood sample collection are in the laboratory manual provided to study sites.

Samples for laboratory testing will be collected at time points according to [Section 1.2](#). Tests will include

- Blood chemistry: sodium, potassium, chloride, carbon dioxide, calcium, glucose, albumin, total protein (serum), creatinine, blood urea nitrogen, aspartate aminotransferase (AST), alanine aminotransferase (ALT), alkaline phosphatase, lactate dehydrogenase (LDH), total bilirubin, total cholesterol, low-density lipoprotein, high-density lipoprotein, triglycerides, uric acid, creatine phosphokinase (CPK)
Note: Direct and indirect bilirubin will be measured when the total bilirubin is above the upper limit of normal (ULN); CPK isoenzymes will be reflexly measured when CPK >5 ULN.
- Hematology: hemoglobin, hematocrit, red blood cells (RBCs), white blood cells (WBCs) and differential (neutrophils, lymphocytes, monocytes, basophils, eosinophils), red cell indices, platelet count
- Urinalysis: Color, clarity, pH, specific gravity, ketones, protein, glucose, blood, bilirubin, leukocyte esterase, nitrite, WBC, RBC, hyaline and other casts, bacteria, epithelial cells, crystals, yeast
Microscopic analysis will only be done in the event of abnormal dipstick results.
- Pregnancy testing (serum or urine) will be performed for all women of childbearing potential.
- Testing for HIV antibody, HBsAg, HBsAb, HBcAb, HBV DNA (for patients presenting with HBsAg [-] and HBcAb [+]) and hepatitis C antibody, and ANA will be performed at screening
Hepatitis C virus (HCV) RNA testing may be performed to rule out a false positivity, if the Investigator believes the patient is a false positive. Anti-dsDNA antibody will be tested if ANA is positive.

9.2.2.3 *Vital Signs*

Vital signs, including heart rate, blood pressure, body temperature, and respiration rate, will be collected.

9.2.2.4 *Physical examination*

A thorough and complete physical examination will be performed at time points according to [Section 1.2](#). Care should be taken to examine and assess any abnormalities that may be present, as indicated by the patient's medical history. If patients have any symptom or sign of ocular surface diseases, eg, conjunctivitis and blepharitis, at screening or during study period, ophthalmological examinations should be done.

9.2.2.5 *Weight and Height*

Weight and height will be determined at time points according to [Section 1.2](#).

9.2.2.6 ECG

Electrocardiograms will be performed before blood is drawn during visits requiring blood draws. A standard 12-lead ECG will be performed at time points according to [Section 1.2](#). The ECG strips or reports will be retained with the source documentation, and the results will be documented in the electronic case report form (eCRF).

9.2.2.7 Immunogenicity

Anti-drug antibody measurements:

Samples for ADA assessment will be collected at time points listed in [Section 1.2](#).

Anti-drug antibody variable definition:

- Negative in ADA assay at all time points analyzed
- Preexisting immunoreactivity (defined as either an ADA positive response in the ADA assay at baseline with all post first dose ADA results negative, OR a positive response at baseline in the ADA assay with all post first dose ADA results less than 4-fold baseline titer levels)
- Treatment emergent response in the ADA assay (defined as a positive response in the ADA assay post first dose when baseline results are negative or missing). The treatment emergent responses may be further characterized as
 - Persistent (defined as treatment emergent ADA positive response with two or more consecutive ADA positive sampling time points separated by greater than 12-week period [greater than 85 days], with no ADA negative samples or any missing sample in between)
 - Indeterminate (defined as treatment-emergent response with only the last collected sample positive in the ADA assay)
 - Transient (defined as treatment emergent ADA positive response that is not considered persistent or indeterminate)
- Treatment boosted response in the ADA assay (defined as a positive response in the ADA assay post first dose that is greater than or equal to 4-fold over baseline titer levels, when baseline results are positive)

ADA titer value category definition:

- Low (titer <1000)
- Moderate ($1000 \leq \text{titer} \leq 10\,000$)
- High (titer >10 000)

All samples that are positive in the ADA assay will be further tested for the presence of anti-dupilumab neutralizing antibodies.

Descriptive statistics for the incidence of anti-dupilumab antibodies response variables will be summarized for the ADA population. Listings of anti-dupilumab antibody status, neutralizing status, and titers per time point and treatment group will be provided.

Plots of concentrations of functional dupilumab will be examined and the potential influence of ADA on individual concentration-time profiles will be evaluated. Assessment of the potential impact of ADA on safety and efficacy may be provided.

9.3 OTHER ENDPOINTS

9.3.1 Pharmacokinetics parameters

9.3.1.1 *Pharmacokinetic measurements*

Samples for measurement of functional dupilumab concentration in serum will be collected at time points listed in [Section 1.2](#).

9.3.1.2 *Pharmacokinetic parameters*

The PK variables may include, but are not limited to, the following:

- C_{trough} over time

[REDACTED]

[REDACTED]

[REDACTED]

[REDACTED]

[REDACTED]

[REDACTED]

9.4 FUTURE USE OF SAMPLES

Not applicable.

9.5 APPROPRIATENESS OF MEASUREMENTS

The efficacy and safety assessments used in this study are standard for the evaluation of therapy in patients with AD.

10 STUDY PROCEDURES

10.1 VISIT SCHEDULE

Study assessments and procedures are presented by study period and visit in [Table 1](#).

Assessments/procedures at a clinic visit should be performed in the following order:

1. Patient reported outcomes.
2. Investigator assessments (performed only by adequately trained Investigators or sub-Investigators; the same Investigator or sub-Investigator should perform all the evaluations for a given patient throughout the entire study period).
3. Safety and laboratory assessments.
4. Administration of the IMP.

10.1.1 Visit 1/Screening/Day -7 to -35

After the patient has provided informed consent, the following information will be collected:

- Inclusion/exclusion
- Medical history and concurrent illnesses
- Demographics
- Concomitant medications/procedures
- AEs

The following procedures and assessments will be conducted:

- Training on the pruritus reporting system
- Pruritus NRS and pruritus categorical scale
- All questionnaires will be administered before any invasive procedures
 - Patient oriented eczema measure (POEM)
 - Dermatology life quality index (DLQI)
- Vital signs
- IGA
- EASI
- BSA involvement of AD
- Weight
- Height
- Physical examination (If patients have any symptom or sign of ocular surface diseases, eg, conjunctivitis and blepharitis, at screening or during study period, ophthalmological examinations should be done.)
- ECG

- Laboratory testing:
 - HIV ab
 - HBsAg, HBsAb, HBcAb, HBV DNA testing should be done for patients presenting with HBsAg (-) and HBcAb (+)
 - Hepatitis C antibody (in case of results showing HCV Ab positive, an HCV RNA testing may be performed to rule out a false positivity, if the Investigator believes the patient is a false positive)
 - Hematology and chemistry
 - Urinalysis
 - Serum pregnancy test (WOCBP only)
 - [REDACTED]
 - [REDACTED]
 - Anti-nuclear antibody (ANA)
 - Anti-dsDNA (only for ANA positive patients)

10.1.2 Treatment Period

10.1.2.1 Visit 2/Baseline/Day 1 (Randomization)

The following information will be collected:

- Inclusion/Exclusion
- Concomitant medications/procedures
- AEs

The following procedures and assessments will be conducted:

- Pruritus NRS and pruritus categorical scale
- All questionnaires will be administered before any invasive procedures:
 - POEM
 - DLQI
 - EQ-5D
- Assess sick leave/missed school days
- Vital signs
- IGA
- EASI
- BSA
- Photograph AD area (select sites only)
- Weight
- Laboratory testing:
 - Hematology and chemistry
 - Urinalysis
 - Urine pregnancy test (WOCBP only)

- Functional dupilumab pharmacokinetic (PK) sample
- Anti-dupilumab antibody sample
- Randomization
- Administer the IMP after all the other assessments have been performed. Train patient/caregiver in injection technique if the patient chooses to self-administer the IMP at selected weeks.
 - The patient will be monitored in the clinic for at least 30 minutes after the injection for any signs or symptoms of a hypersensitivity reaction. In addition to the predose assessments, AE assessments will be done at 30 minutes (± 10 minutes) postinjection.

10.1.2.2 Visit 3/Week 2/Day 15 (± 3 days)

The following information will be collected:

- Concomitant medications/procedures
- AEs

The following procedures and assessments will be conducted:

- Pruritus NRS and pruritus categorical scale
- All questionnaires will be administered before any invasive procedures:
 - POEM
 - DLQI
- Vital signs
- IGA
- EASI
- BSA
- Administer the IMP after all the other assessments have been performed. Train patient/caregiver in injection technique if the patient chooses to self-administer the IMP at selected weeks.
 - The patient will be monitored in the clinic for at least 30 minutes after the injection for any signs or symptoms of a hypersensitivity reaction. In addition to the predose assessments, AE assessments will be done at 30 minutes (± 10 minutes) postinjection

10.1.2.3 Visit 4/Week 4/Day 29 (± 3 days)

The following information will be collected:

- Concomitant medications/procedures
- AEs

The following procedures and assessments will be conducted:

- Pruritus NRS and pruritus categorical scale

- All questionnaires will be administered before any invasive procedures:
 - POEM
 - DLQI
- Assess sick leave/missed school days
- Vital signs
- IGA
- EASI
- BSA
- Laboratory testing:
 - Urine pregnancy test (WOCBP only)
- Administer the IMP after all the other assessments have been performed. Train patient/caregiver in injection technique if the patient chooses to self-administer the IMP at selected weeks.
 - The patient will be monitored in the clinic for at least 30 minutes after the injection for any signs or symptoms of a hypersensitivity reaction. In addition to the predose assessments, AE assessments will be done at 30 minutes (± 10 minutes) postinjection
- Dispense the patient dosing diary and the IMP for Week 6 if the patient chooses to self-inject at home at Week 6.

10.1.2.4 Visit 5/ Week 8/Day 57 (± 3 days)

The following information will be collected:

- Concomitant medications/procedures
- AEs
- If the patient chose to self-inject the IMP on Week 6, review the patient dosing diary and account for the IMP. Collect any unused IMP.

The following procedures and assessments will be conducted:

- Pruritus NRS and pruritus categorical scale
- All questionnaires will be administered before any invasive procedures:
 - POEM
 - DLQI
 - EQ-5D
- Assess sick leave/missed school days
- Vital signs
- IGA
- EASI
- BSA
- Laboratory testing:
 - Hematology and chemistry
 - Urine pregnancy test (WOCBP only)

- Administer the IMP after all the other assessments have been performed. Train patient/caregiver in injection technique (if needed) if the patient chooses to self-administer the IMP at selected weeks.
 - The patient will be monitored in the clinic for at least 30 minutes after the injection for any signs or symptoms of a hypersensitivity reaction. In addition to the predose assessments, AE assessments will be done at 30 minutes (± 10 minutes) postinjection
- Dispense the patient dosing diary and the IMP for Week 10 if the patient chooses to self-inject at home at Week 10.

10.1.2.5 Visit 6/Week 12/Day 85 (± 3 days)

The following information will be collected:

- Concomitant medications/procedures
- AEs
- If the patient chose to self-inject the IMP on Week 10, review the patient dosing diary and account for the IMP. Collect any unused IMP.

The following procedures and assessments will be conducted:

- Pruritus NRS and pruritus categorical scale
- All questionnaires will be administered before any invasive procedures:
 - POEM
 - DLQI
- Assess sick leave/missed school days
- Vital signs
- IGA
- EASI
- BSA
- Laboratory testing:
 - Urine pregnancy test (WOCBP only)
 - Functional dupilumab PK sample
 - Anti-dupilumab antibody sample
- Administer the IMP after all the other assessments have been performed. Train patient/caregiver in injection technique (if needed) if the patient chooses to self-administer the IMP at selected weeks.
 - The patient will be monitored in the clinic for at least 30 minutes after the injection for any signs or symptoms of a hypersensitivity reaction. In addition to the predose assessments, AE assessments will be done at 30 minutes (± 10 minutes) postinjection
- Dispense the patient dosing diary and the IMP for Week 14 if the patient chooses to self-inject at home at Week 14.

10.1.2.6 Visit 7/End of Treatment/Week 16/Day 113 (± 3 days)

The following information will be collected:

- Concomitant medications/procedures
- AEs
- If the patient chose to self-inject the IMP on Week 14, review the patient dosing diary and account for the IMP. Collect any unused IMP.

The following procedures and assessments will be conducted:

- Pruritus NRS and pruritus categorical scale
- All questionnaires will be administered before any invasive procedures:
 - POEM
 - DLQI
 - EQ-5D
- Assess sick leave/missed school days
- Vital signs
- IGA
- EASI
- BSA
- Photograph AD area (select sites only)
- Weight
- Physical examination
- ECG
- Laboratory testing:
 - Hematology and chemistry
 - Urinalysis
 - Serum pregnancy test (WOCBP only)
 - [REDACTED]
 - Functional dupilumab PK sample
 - Anti-dupilumab antibody sample

10.1.3 Follow-up Period

10.1.3.1 Visit 8/Week 20/Day 141 (± 3 days)

The following information will be collected:

- Concomitant medications/procedures
- AEs

The following procedures and assessments will be conducted:

- Pruritus NRS and pruritus categorical scale
- POEM
- DLQI
- Assess sick leave/missed school days
- Vital signs
- IGA
- EASI
- BSA

10.1.3.2 Visit 9/Week 24/Day 169 (± 3 days)

The following information will be collected:

- Concomitant medications/procedures
- AEs

The following procedures and assessments will be conducted:

- Pruritus NRS and pruritus categorical scale
- POEM
- DLQI
- Assess sick leave/missed school days
- Vital signs
- IGA
- EASI
- BSA

10.1.4 Visit 10/End of Study Visit/Week 28/Day 197 (± 3 days)

The following information will be collected:

- Concomitant medications/procedures
- AEs

The following procedures and assessments will be conducted:

- Pruritus NRS and pruritus categorical scale
- POEM
- DLQI
- EQ-5D
- Assess sick leave/missed school days
- Vital signs
- IGA
- EASI

- BSA
- Photograph AD area (select sites only)
- Weight
- Physical examination
- ECG
- Laboratory testing:
 - Hematology and chemistry
 - Urinalysis
 - Serum pregnancy test (WOCBP only)
 - Functional dupilumab PK sample
 - Anti-dupilumab antibody sample

10.1.5 Early Termination Visit

Patients who are withdrawn from the study before the primary endpoint visit (Week 16) will be asked to return to the clinic for 2 visits: once for early termination assessments, and again at Week 16 (primary endpoint visit), as described in [Section 10.1.2.6](#). Patients who are withdrawn from the study after the primary endpoint visit will be asked to return to the clinic for early termination assessments.

The following information will be collected:

- Concomitant medications/procedures
- AEs

The following procedures and assessments will be conducted:

- Pruritus NRS and pruritus categorical scale
- POEM
- DLQI
- EQ-5D
- Assess sick leave/missed school days
- Vital signs
- IGA
- EASI
- BSA
- Photograph AD area (select sites only)
- Weight
- Physical examination
- ECG
- Laboratory testing:
 - Hematology and chemistry

- Urinalysis
- Serum pregnancy test (WOCBP only)
[REDACTED]
[REDACTED]
- Functional dupilumab PK sample
- Anti-dupilumab antibody sample

10.1.6 Unscheduled Visits

All attempts should be made to keep patients on the study schedule. Unscheduled visits may be necessary to repeat testing following abnormal laboratory results, for follow-up of AEs, or for any other reason, as warranted. During an unscheduled visit, any of the procedures noted may be performed, but not all are required.

The following information will be collected:

- Concomitant medications/procedures
- AEs

The following procedures and assessments will be conducted:

- Pruritus NRS and pruritus categorical scale
- POEM
- DLQI
- Assess sick leave/missed school days
- Vital signs
- IGA
- EASI
- BSA
- Photograph AD area (select sites only)
- Weight
- Laboratory testing:
 - Hematology and chemistry
 - Urinalysis
 - Urine pregnancy test (WOCBP only)
[REDACTED]
[REDACTED]
 - Functional dupilumab PK sample
 - Anti-dupilumab antibody sample

10.2 DEFINITION OF SOURCE DATA

Source data is all information in original records and certified copies of original records of clinical findings, observations, or other activities in a clinical trial necessary for the reconstruction and evaluation of the trial. Source data are contained in source documents. Source documents are original documents, data and records such as hospital records, clinic and office charts, laboratory notes, memoranda, pharmacy dispensing records, recorded data from automated instruments, etc.

All the data collected in the e-CRF should be transcribed directly from source documents. Data downloaded from the study-associated central laboratories and patient electronic diary will be considered source data.

10.3 HANDLING OF PATIENT TEMPORARY OR PERMANENT TREATMENT DISCONTINUATION AND OF PATIENT STUDY DISCONTINUATION

The IMP should be continued whenever possible. In case the IMP is stopped, it should be determined whether the stop can be made temporarily; permanent IMP discontinuation should be a last resort. Any IMP discontinuation should be fully documented in the CRF. In any case, the patient should remain in the study as long as possible.

10.3.1 Temporary treatment discontinuation with investigational medicinal products

Temporary treatment discontinuation may be considered by the Investigator because of AEs. Reinitiation of treatment with the IMP will be done under close and appropriate clinical/and or laboratory monitoring once the Investigator considers, according to his/her best medical judgment, that the AE is sufficiently resolved and unlikely to recur after resuming therapy with the IMP.

The following condition(s) will be causes for temporary treatment discontinuation:

- Any laboratory abnormality that meets temporary treatment discontinuation criteria as per [Appendix E](#)
- Other intercurrent illnesses or major surgery
- Infections or infestations that do not respond to medical treatment
The IMP should be discontinued until the infection is resolved.
- Treatment with prohibited concomitant medication or procedure as described in [Section 8.8.1](#)

After the lab abnormality leading to suspension of dosing normalizes sufficiently, the IMP may be resumed at the discretion of the principal Investigator in consultation with the sponsor. Similarly, the IMP may be resumed after the medication leading to suspension of dosing is discontinued. A decision to discontinue the IMP and/or to reinstitute the IMP should be discussed with the sponsor. The Investigator may suspend the IMP at any time, even without consultation with the sponsor if the urgency of the situation requires immediate action and if this is determined to be in the patient's best interest. However, the sponsor should be contacted as soon as possible in any case of the IMP discontinuation. Resumption of study treatment after temporary discontinuation should always be discussed with the sponsor.

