8.1.4 Dose modification and investigational medicinal product discontinuation rules

8.1.4.1 Drug modification

Dose modification for an individual patient is not allowed.

8.1.4.2 *Investigational medicinal product discontinuation*

Patients who temporarily or permanently discontinue from the IMP and who do not withdraw from the study will be asked to return to the clinic for all remaining study visits and complete all study assessments per the study schedule. The reasons for temporarily or permanently discontinuation of the IMP are described in [Section 10.3](#).

Patients who opt to withdraw from the study will be asked to complete study assessments, per [Section 10.1.5](#).

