If medically necessary (ie, to control intolerable AD symptoms), rescue treatment for AD with otherwise prohibited medications or procedure (see [Section 8.8.1](#)) may be provided to study patients at the discretion of the Investigator. Please refer to the label of the product for the usage of rescue treatment. For the purpose of efficacy analysis, patients who receive rescue treatment during the study treatment period will be considered treatment failures, but they will continue study treatment if rescue consisted of topical medications. Topical calcineurin inhibitors may be used for rescue, but should be reserved for problem areas only, eg, face, neck, intertriginous, and genital areas. If possible, Investigators should attempt to limit the first step of rescue therapy to topical medications, and escalate to systemic medications only for patients who do not respond adequately after at least 7 days of topical treatment. If a patient receives rescue treatment with systemic corticosteroids or nonsteroidal systemic immunosuppressive/immunomodulating drugs (cyclosporine, methotrexate, mycophenolate mofetil, azathioprine, Janus kinase inhibitors, biologic agents, etc), the IMP will be immediately discontinued. After the treatment with these medications is completed, the IMP may be resumed if deemed appropriate by the Investigator and the sponsor, but not sooner than 5 half-lives after the last dose of systemic rescue medication. All patients will complete the schedule of study visits and assessments whether or not they complete the treatment with the IMP and whether or not they receive rescue treatment for AD. Investigators should make every attempt to conduct efficacy and safety assessments (eg, disease severity scores, safety labs) immediately before administering any rescue treatment. An unscheduled visit may be used for this purpose if necessary.

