8.8.1 Prohibited medications and procedures

The following treatments are prohibited during the study:

- Treatment with a live (attenuated) vaccine (See [Appendix B](#))
- Treatment with immunomodulating biologics
- Treatment with an investigational drug (other than dupilumab)
- Treatment with TCS or TCI
- Treatment with systemic corticosteroids or nonsteroidal systemic immunosuppressive/immunomodulating drugs (eg, cyclosporine, methotrexate, mycophenolate-mofetil, azathioprine, and Janus kinase inhibitors)
- Initiation or uptitration of allergen-specific immunotherapy (SIT). Patients on SIT prior to the screening visit must be on a stable dose and remain on that dose during the study
- Any other medications for AD that could have interfered with efficacy outcomes or affected the evaluation for AD severity. Examples of such medications include coal tar products, other staining topical products, TCM, or any other therapeutic agents for AD that were not properly evaluated in clinical trials

However, at the discretion of the Investigator, patients were permitted to receive rescue treatment with some of the otherwise prohibited medications noted below. Rescue treatment (see [Section 8.2.2](#) for details) is only to be performed when medically necessary for worsening AD signs and/or symptoms requiring initiation or escalation of treatment.

The IMP will be discontinued if the following is used through Week 16:

- Treatment with a live (attenuated) vaccine
- Treatment with immunomodulating biologics
- Treatment with an investigational drug (other than dupilumab)
- Treatment with systemic corticosteroids or nonsteroidal systemic immunosuppressive/immunomodulating drugs (eg, cyclosporine, methotrexate, mycophenolate-mofetil, azathioprine, and Janus kinase inhibitors)

If a patient receives treatment with systemic corticosteroids or other systemic immunosuppressive/immunomodulating drugs (cyclosporine, methotrexate, mycophenolate mofetil, azathioprine, Janus kinase inhibitors, biologic agents, etc), the IMP will be immediately discontinued. After the treatment with these medications is completed, the IMP may be resumed if deemed appropriate by the Investigator and the sponsor, but not sooner than 5 half-lives after the last dose of systemic rescue medication.

The following concomitant procedures are prohibited during study participation:

- Major elective surgical procedures
- Phototherapy except as rescue for AD
- Tanning in a bed/booth

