- Treatment with systemic corticosteroids or nonsteroidal systemic immunosuppressive/immunomodulating drugs (eg, cyclosporine, methotrexate, mycophenolate-mofetil, azathioprine, and Janus kinase inhibitors)

The following concomitant procedures are prohibited during study participation:

- Major elective surgical procedures
- Phototherapy
- Tanning in a bed/booth

Rescue treatments for AD: If medically necessary (ie, to control intolerable AD symptoms), rescue treatment for AD with otherwise prohibited medication or procedure may be provided to study patients at the discretion of the investigator.

Patients who receive rescue treatment during the study treatment period will continue study treatment if rescue consisted of topical medications. Topical calcineurin inhibitors may be used for rescue, but should be reserved for problem areas only. If possible, Investigators should attempt to limit the first step of rescue therapy to topical medications, and escalate to systemic medications only for patients who do not respond adequately after at least 7 days of topical treatment.

If a patient receives rescue treatment with systemic corticosteroids or nonsteroidal systemic immunosuppressive/immunomodulating drugs (cyclosporine, methotrexate, mycophenolate mofetil, azathioprine, Janus kinase inhibitors, biologic agents, etc), the IMP will be immediately discontinued.

After the treatment with these medications is completed, the IMP may be resumed if deemed appropriate by the Investigator and the sponsor, but not sooner than 5 half-lives after the last dose of systemic rescue medication.

All patients will complete the schedule of study visits and assessments whether or not they complete the treatment with the IMP and whether or not they receive rescue treatment for AD. Investigators should make every attempt to conduct efficacy and safety assessments (eg, disease severity scores, safety labs) immediately before administering any rescue treatment. An unscheduled visit may be used for this purpose if necessary.

Blinded adjudication of rescue treatments will be implemented before database locks by considering the type of medication, indication, timing, frequency and the potential impact of the use of the prohibited medication or procedure. The rescue treatments will be adjudicated by the clinical study director and the adjudication procedure will be documented.

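### The suspension rule in Protocol 10.3.1 omits the topical-rescue exception that Protocol 8.2.2 and SAP 4.3 state

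*Protocol*

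**What the plan says.** Protocol 10.3.1 lists conditions that are to lead to temporary discontinuation of the IMP. One is "Treatment with prohibited concomitant medication or procedure as described in" Section 8.8.1. The bullet has no exception. Protocol 8.1.4.2 sends the reader to this part of the protocol: "The reasons for temporarily or permanently discontinuation of the IMP are described in" Section 10.3.

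The prohibited list in Protocol 8.8.1 includes "Treatment with TCS or TCI" (topical corticosteroids, topical calcineurin inhibitors). Further down, 8.8.1 says that, at the investigator's discretion, "patients were permitted to receive rescue treatment with some of the otherwise prohibited medications noted below", and refers to 8.2.2. It then gives a separate, shorter list under the words "The IMP will be discontinued if the following is used through Week 16". TCS and TCI are not on that list.

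Protocol 8.2.2 says of rescued patients that "they will continue study treatment if rescue consisted of topical medications". SAP 4.3 says the same: "Patients who receive rescue treatment during the study treatment period will continue study treatment if rescue consisted of topical medications". Both reserve immediate discontinuation for systemic rescue. Section 10.3 itself opens with "The IMP should be continued whenever possible".

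**The concern.** For one event, a patient starting a rescue course of TCS or TCI, the protocol gives two answers. Section 8.2.2 says keep dosing. The 10.3.1 bullet, taken at its word, says suspend. Topical treatment is also the first rescue step that 8.2.2 asks investigators to try, so the conflict falls on the preferred route.

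A site that followed the bullet would withhold doses for the length of the topical course, since 10.3.1 allows dosing to resume once the medication that led to suspension is stopped. The missed doses could then affect:

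- per-protocol (PP) membership, through the 80% compliance limit (Protocol 11.3.1, SAP 3.2);
- the Week 12 and Week 16 trough concentrations (SAP 4.6);
- the sensitivity analyses that use all observed data regardless of rescue (SAP 5.7.1 and 5.7.2).

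**Working it through.** The plan gives no figure on this point. Its 94% power does not depend on it, and it reproduces as 94.5% with 80 per arm, 37% versus 12%, two-sided 0.05 and continuity correction.

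**Which analyses can change.** Under SAP 5.7.1 a rescued patient is a non-responder from the time of rescue. Under SAP 5.7.2 later continuous data are set to missing and imputed. Neither rule depends on whether the IMP was continued, so for topical use that counts as rescue the primary and main continuous results are the same either way. The PP set, the troughs and the all-observed-data analyses do depend on doses given or on post-rescue data.

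**Inputs for the dose count**

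- Target dosing days 1, 15, 29, 43, 57, 71, 85 and 99 (Protocol Table 1). This is 8 occasions, with the loading dose counted as one (SAP 5.5).
- A 3-day window either side of the target and at least 11 days between doses (Protocol 8.1.3).
- PP limit: 80% of scheduled doses (Protocol 11.3.1).
- Course length, assumed: 7 days is the only duration in 8.2.2, where it is a minimum before escalation. The 14 and 28 days are borrowed from I 07, which defines prior topical failure and not rescue.
- Also assumed: one course per patient, and the IMP resumes as soon as the course ends.

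**Rule.** A course of L days starting on Day s covers Days s to s + L − 1.

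- Late window only: the dose with target T is lost if s ≤ T and s + L − 1 ≥ T + 3. That is L − 3 start days per dose.
- Full ±3-day window: the dose is lost if s ≤ T − 3 and s + L − 1 ≥ T + 3. That is L − 6 start days per dose. This is a best case, because it treats the dose as already given early before an unforeseen course.

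The 11-day gap does not bind: a dose on T + 3 is 11 days before the next target, and a dose on T − 3 is 11 days after the previous one.

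**Results** (7 doses after Day 1, hence 6 adjacent pairs)

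| Course | Start days | Outcome | Late window only | Full window |
|---|---|---|---|---|
| 7 days | 2–99 | loses one | 4 × 7 = 28 of 98 | 1 × 7 = 7 of 98 |
| 14 days | 2–99 | loses one | 11 × 7 = 77 of 98 | 8 × 7 = 56 of 98 |
| 28 days | 2–85 | loses two | 11 × 6 = 66 of 84 | 8 × 6 = 48 of 84 |
| 28 days | 86–99 | loses one | 14 of 14 | 11 of 14 |

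For the 28-day course on Days 2–85, both doses of a pair (T, T + 14) are lost if s runs from T − 10 to T (11 days), or from T − 10 to T − 3 (8 days) with the full window. The remaining 18 or 36 start days lose one dose. In the other rows, the remaining start days lose none. The 7-day and 14-day courses never lose two.

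**Compliance.** One dose missed: 7/8 = 87.5%, so the patient stays in PP. Two missed: 6/8 = 75%, below 80%. To lose two doses, a single course must span T to T + 17, which is 18 days (late window), or T − 3 to T + 17, which is 21 days (full window).

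In 11 of the 66 late-window cases (starts on Days 75 to 85) the Week 12 and Week 14 doses are lost and dosing never restarts. The exposure-period formula in SAP 5.5 then gives 6/6 = 100%, against 6/8 = 75% of scheduled doses.

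**Troughs.** If the Week 10 dose is missed, the nominal time from last dose to the Week 12 sample is 85 − 57 = 28 days instead of 85 − 71 = 14. If the Week 14 dose is missed, the time to the Week 16 sample is 113 − 85 = 28 days instead of 113 − 99 = 14.

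**The case against.** The strongest reply is that the cross-reference already resolves the matter. A site that follows the bullet to 8.8.1 finds the rescue permission, the pointer to 8.2.2 and a stop list without TCS or TCI. The rule in 8.2.2 is specific and SAP 4.3 repeats it. Section 10.3 favours continuing the IMP. Section 10.3.1 also says that a decision to discontinue should be discussed with the sponsor, and it lets the investigator act alone only in urgent cases.

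All of this stands as evidence of intent and as a reason to expect few errors. It does not remove the contradiction. The bullet cites 8.8.1 as a whole and covers procedures, none of which is on the stop list, so it cannot be read as a pointer to that list alone. Rescue drugs remain described as otherwise prohibited. And 8.1.4.2 sends sites to 10.3 for the discontinuation reasons, which is where the exception is missing.

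It is also fair to object that 14-day and 28-day courses are not rescue durations from the plan and that short courses do little harm. That stands, and it is why the 7-day case and both windows are shown.

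**Conclusion.** The 10.3.1 bullet is wrong as written, and the point is minor. Its intent is clear, but its literal instruction contradicts 8.2.2 and SAP 4.3 on when dosing stops.

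The size depends on a misreading that sponsor contact does not correct, and on the assumed course lengths. Of the three lengths, only 28 days can take a patient below the PP limit through a single course. A 7-day course usually costs nothing. The documents give no rescue rate, so no number of patients can be stated, and the counts above are possible start days, not probabilities.

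Two stronger readings are not supported. A reader might infer that the sponsor means topical rescue to suspend the IMP; 8.2.2, SAP 4.3 and the stop list in 8.8.1 say otherwise. A reader might also infer that the primary result is at risk; the non-responder and set-to-missing rules make it indifferent to dosing after rescue. What could change is supportive (PP), descriptive (troughs) or a sensitivity analysis.

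**What to change.** Keep the reference to 8.8.1 and add to the 10.3.1 bullet: *except topical rescue treatment under Section 8.2.2, during which the IMP continues*.

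Do not narrow the bullet to the stop list in 8.8.1. That would remove the suspension trigger for treatments that are prohibited but not on that list: traditional Chinese medicine, newly started allergen-specific immunotherapy, phototherapy outside rescue, and tanning.

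The cost is one sentence in an amendment or clarification, with ethics committee handling as Protocol Section 15 requires. No new data or analyses are needed, and the SAP needs no change.
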